1.2 Comparison with Healthy Children and Other Chronic Illnesses

In contrast, healthy children generally experience more consistent and undisturbed sleep accentuates how chronic illnesses combined with hospitalization damage children's sleep quality. Children with other chronic illnesses also encounter sleep difficulties yet their reasons for these issues differ from those diagnosed with cancer. For instance, the condition of asthma triggers nighttime awakenings because of wheezing and coughing, while diabetic patients experience disrupted sleep due to fluctuating glucose levels (Adavadkar et al., 2022; Meltzer & Mindell, 2017). These conditions cause sleep interference but patients tend to experience less psychological and physical distress from cancer which leads to milder overall sleep issues.

2. Study Objectives

The objectives of this study are threefold:

- 1) To assess the prevalence and nature of sleep disturbances in children with cancer.
- 2) To compare sleep disturbances in children with cancer to those in healthy children and children with other chronic diseases.
- 3) To identify potential factors contributing to sleep disturbances in paediatric patients.

3. Study Significance

This study contributes to the comprehension of pediatric sleep disturbances by carefully evaluating sleep disruptions among three groups: children with cancer, children with other chronic illnesses, and healthy children. The data generated from this study provides vital information for developing targeted therapies specific to population groups with linked sleep disturbance factors. By pinpointing specific contributors, such as hospital environment, medication effects, or pain, the research will lay the groundwork for targeted interventions. These could include reducing nighttime disruptions, refining pain management, or designing sleep-friendly hospital settings. Furthermore, integrating tools like the Chinese version of PSQI into routine care could enable early detection and management of sleep issues, mitigating long-term risks like cognitive and emotional deficits

Beyond oncology, the study's comparison with children who have other chronic illnesses will reveal how different conditions uniquely disrupt sleep, guiding tailored strategies for diverse patient groups. The healthy control group will establish a benchmark for normal sleep, highlighting the extent of disruption caused by chronic illness and elevating sleep as a priority in pediatric care.

4. Methods

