4.1 Study Design

A prospective and cross-sectional study will be conducted to examine and compare sleep problems in three groups of children: 1) healthy children, 2) children with various chronic illnesses and undergoing active treatment, and 3) children with cancer and undergoing active treatment. This research design allows for a one-time analysis of sleep characteristics and factors that contribute to disturbances in

three pediatric groups. The study aims to reveal distinct sleep disturbance characteristics of each examined group to determine how sleep changes relate to cancer and other medical conditions among individuals. Such research design allows effective assessment through simultaneous analysis to acquire an in-depth overview of sleep health dynamics among all groups.

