4.2.1 The Chinese version of Pittsburgh Sleep Quality Index (PSQI)

The PSQI is a widely validated self-report questionnaire designed to evaluate sleep quality and disturbances (Mollayeva et al., 2016). Although originally developed for adults, it has been adapted and used effectively in pediatric populations with parental assistance for younger children (De La Vega et al., 2015; Tietze et al., 2014). The Chinese version of the PSQI, as validated for use in Hong Kong Chinese populations, including childhood cancer survivors, retains the same structure as the original PSQI (Ho et al., 2021). The PSQI consists of 19 self-rated questions and 5 questions rated by a bed partner or roommate. The 19 self-rated questions are grouped into 7 component scores: subjective sleep quality, sleep latency, sleep duration, habitual sleep efficiency, sleep disturbances, use of sleep medication, and daytime dysfunction. Each component is scored from 0 to 3, contributing to a global score ranging from 0 to 21. The Chinese version of the PSQI is completed by parents for younger children (e.g., aged 6-11) or by children aged 12-18 with parental assistance if needed. The PSQI's multidimensional approach will provide detailed insights into specific aspects of sleep disruption, such as prolonged sleep onset or frequent awakenings, particularly relevant to hospitalized children with cancer.

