4.2.2 The Chinese version of Pediatric Quality of Life Inventory 4.0 (PedsQL 4.0)

The PedsQL is a well-established instrument for assessing health-related quality of life in children and adolescents aged 2-18 years (Varni et al., 2005). This study will use the Chinese version of PedsQL 4.0 Generic Core Scales, which include 23 items across four domains: physical functioning (8 items), emotional functioning (5 items), social functioning (5 items), and school functioning (5 items). Responses are scored on a 5-point Likert scale (0 = never a problem, 4 = almost always a problem), then transformed to a 0-100 scale, where higher scores reflect better health-related quality of life. The PedsQL yields a total scale score (average of all 23 items), a physical health summary score (average of the 8 physical functioning items), and a psychosocial health summary score (average of the 15 items across emotional, social, and school functioning domains). These scores provide a comprehensive assessment of overall quality of life and specific physical and psychosocial

health outcomes, enabling exploration of how sleep disturbances correlate with broader well-being in children with cancer, other chronic illnesses, and healthy controls. Parent-proxy reports for younger children and self-reports for older participants, mirroring the PSQI administration. The PedsQL 4.0 Generic Core Scale has undergone cross-cultural adaptation into Chinese and psychometric validation, rendering it suitable for application in clinical settings (Ji et al., 2011; Yeung et al., 2012). The Chinese version of PedsQL will serve as a secondary measure to explore how sleep disturbances correlate with broader quality-of-life outcomes, such as fatigue-related physical limitations or emotional distress, which are particularly pertinent to children with chronic illnesses like cancer.

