4.3.3 Demographic Variables

To control for potential confounding effects on sleep patterns and access to healthcare resources, the following demographic and clinical variables will be collected: age (in years), gender, socioeconomic status (SES), disease type, disease status, and use of hypnotics (yes/no). SES will be assessed through parental education (categorized as primary or below, junior secondary, senior secondary, or university/college and above). For children with cancer, disease type (e.g., leukemia, lymphoma, brain tumor, bone tumor, or others) and disease status (e.g., stage 1-4, recurrence, years since diagnosis, treatment type such as chemotherapy, radiotherapy, surgery, immunotherapy, transplant, or combination) will be recorded. For children with other chronic illnesses, disease type (e.g., asthma, type 1 diabetes, chronic kidney disease) will be noted. These factors may influence sleep outcomes, e.g., older children may report greater daytime dysfunction, or lower parental education level may limit access to supportive care, necessitating adjustment in statistical analyses to isolate the effects of chronic illness on sleep quality.

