Data will be analyzed using SPSS (version 29), a powerful statistical software package designed for clinical research. Descriptive statistics such as means, standard deviations, and frequencies, will summarize demographic characteristics (e.g., age, gender distribution), as well as PSQI global and component scores, and PedsQL total and subscale scores for each group. To compare sleep quality and health-related quality of life across the three groups, a one-way analysis of variance (ANOVA) will be used for continuous variables (e.g., PSQI global score, sleep duration, PedsQL physical functioning score). For secondary analyses, multiple linear regression will examine the relationships between sleep quality (PSQI score) and potential predictors (e.g., type of cancer treatment, pain levels) while adjusting for confounding factors such as age, gender, and socioeconomic status (SES). Pearson or Spearman correlations will be utilized to assess the relationships between PSQI and PedsQL scores, helping to evaluate the impact of sleep disturbances on health-related quality of life. A p-value of less than 0.05 will indicate statistical significance, and effect sizes (e.g., eta-squared) will be reported to quantify the magnitude of differences.

8. Parental Consent and Children's Assent

Ensuring the ethical participation of children in this study requires a dual approach, involving obtaining informed consent from parents or legal guardians and, where appropriate, obtaining assent from the children themselves.

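### Section 7 names pain as a predictor of sleep quality and Section 3 promises to pinpoint pain and hospital environment, but the protocol specifies no measure of either

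*Protocol*

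**What the plan says.** Objective 3 in Section 2 is "To identify potential factors contributing to sleep disturbances in paediatric patients". Section 3 gives this practical content: "By pinpointing specific contributors, such as hospital environment, medication effects, or pain, the research will lay the groundwork for targeted interventions". Section 4.1 presents the design as suited to the task: "This research design allows for a one-time analysis of sleep characteristics and factors that contribute to disturbances". Section 7 then regresses PSQI score on "potential predictors (e.g., type of cancer treatment, pain levels) while adjusting for confounding factors", the confounders being age, gender and SES.

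The data behind that regression are described in four places:

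- Section 4.3.3 states that "demographic and clinical variables will be collected: age (in years), gender, socioeconomic status (SES), disease type, disease status, and use of hypnotics (yes/no"). For the cancer group it expands disease status into stage, recurrence, years since diagnosis and treatment type. For the chronic illness group it adds disease type.
- Section 4.2.1 gives the PSQI components as "subjective sleep quality, sleep latency, sleep duration, habitual sleep efficiency, sleep disturbances, use of sleep medication, and daytime dysfunction". Section 4.2.2 describes the PedsQL as "23 items across four domains: physical functioning (8 items), emotional functioning (5 items), social functioning (5 items), and school functioning (5 items").
- Section 6 hands out a demographics form, the PSQI and the PedsQL. Inpatients' forms are collected the same day.
- Section 10 refers in general terms to clinical records among the data collected.

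**The concern.** A predictor that the analysis section names should have a variable behind it. Here the analysis section and the significance section name factors that the data collection sections do not provide for.

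A later analysis plan could not repair this. It can define a model, a coding or a subset, but it cannot supply an answer to a question that was never put to the child or parent. With a single survey during the inpatient stay, a missing pain rating stays missing.

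What is at stake is part of Objective 3. Pain is among the factors that Section 4.4.1 offers for the cancer group's expected poor sleep, and Section 3 names better pain management and sleep-friendly hospital settings as possible interventions. Without a measure, the study could not say whether either factor is associated with sleep.

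**Working it through.** The protocol gives no figure on this point, so the check sets each named factor against each described data source.

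| Data source | What it is stated to yield | Pain measure | Hospital-environment measure |
|---|---|---|---|
| Section 4.3.3 | age, gender, SES, disease type, disease status, hypnotic use | none stated | none stated |
| Section 4.2.1, PSQI | seven sleep components and a global score | none stated | none stated |
| Section 4.2.2, PedsQL | four functioning domains and summary scores | none stated | none stated |
| Section 6, forms | demographics form, PSQI, PedsQL | none stated | none stated |
| Section 10 | clinical records, no field named | not specified, not excluded | not specified, not excluded |

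**Could an existing questionnaire item serve for pain?** The protocol does not reproduce the items and does not say that one is meant. If a PSQI item were used, the predictor would be part of the score it is meant to predict. A pain rating therefore has to stand apart from the PSQI.

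**Could chart data serve?** Possibly, but no scale, rater or time window is given. The documents do not show whether usable scores exist.

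**Could the group contrast stand in for hospital environment?** No. Sections 5.1, 5.2 and 6 make both illness groups inpatients, and Section 5.3 draws the controls from siblings and staff children. Hospitalization therefore coincides with illness. Ward setting largely coincides with illness group, since Section 5.1 uses the oncology wards and Section 5.2 the cardiac, nephrology and mixed wards.

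**What remains answerable?** Age, gender, SES, disease type, disease status (including treatment type for the cancer group) and hypnotic use can all be examined. Medication, the third contributor in Section 3, is at least partly covered by treatment type and hypnotic use.

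**Who would report pain?** Section 4.2.1 has parents complete the PSQI for children of about 6 to 11, while those of 12 to 18 complete it themselves with help if needed. A pain item that follows the PSQI respondent would mix proxy and self-report, so respondent type would need to be recorded and modelled.

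**Separate wording check.** Section 4.4.2 gives the typical absence of hospitalization stressors as one reason for milder sleep problems in the chronic illness group. Section 5.2 requires those children to be currently hospitalized, and Section 6 surveys them during the inpatient stay. These statements do not fit together.

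**The case against.** The strongest reply is that these are open example lists. Section 7 introduces its predictors with an e.g., Section 3 is a statement of significance and not a list of deliverables, and Objective 3 names no factor. Chart sourcing is not ruled out, and text edits alone would cure the mismatch. All of this stands and limits the weight of the point. It does not remove it: a predictor that the protocol chose to name still needs a source, and the opportunity to collect it passes with the survey.

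A reader might infer more than the documents support:

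- *Objective 3 fails altogether.* It does not, because several listed variables bear on it.
- *Recording treatment type only in the cancer group is a further gap.* It is not, since cancer treatment type can exist only for children with cancer.
- *The sample is too small, or large enough, for a pain effect.* The documents give no expected association between pain and sleep and no model terms from which to judge.
- *The Section 4.4.2 conflict undermines the expected difference between cancer and chronic illness.* It does not. Hospitalization is one of several reasons given. Section 4.4.1 relies on pain, chemotherapy side effects and night-time interventions, and Section 1.2 on differing distress. No test or eligibility rule depends on the sentence, and it describes what is typical of the conditions.

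**Conclusion.** The point holds and should be fixed before data collection. Pain has no specified measure in any of the three groups although Section 7 names it as a predictor. Hospital environment likewise has none although Section 3 says it will be pinpointed. As written, the pain term cannot be run and Objective 3 is only partly answerable.

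The effect is confined to a secondary regression and to the claims in Section 3. The global PSQI endpoint, the prevalence of poor sleep and the three-group comparisons do not depend on it.

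The conclusion assumes that the questionnaires yield only what Section 4.2 says they yield, and that the general mention of clinical records does not stand for a defined pain field. If such a field is intended, naming it with its scale, rater and time window would meet much of the pain point.

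The conflict between Section 4.4.2 and Sections 5.2 and 6 is real but is a separate, minor matter of wording.

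**What to change.** **Preferred, before data collection.** Add one simple pain rating to Section 4.3.3 and to the inpatient survey form, separate from the PSQI items. The PSQI respondent should answer it, over the same recall period as the PSQI form in use; the protocol does not state that period and should. Record whether parent or child answered and include that in the model. Use the rating in the secondary regression among the inpatients (50 + 50 = 100 planned). Limit the hospital-environment wording in Section 3 to what is recorded.

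**Cost.** One extra item per inpatient and a form revision for the IRB, with no extra participants or visits. Against the 19 self-rated PSQI and 23 PedsQL items, one item adds 1/42, or about 2.4%, and less once the demographics form is counted. The main drawback is interpretive: when one person reports both pain and sleep, the association may look stronger than it is.

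**If no item is added.** Delete pain from the predictors in Section 7 and restrict Section 3 to the recorded factors. This costs only text edits but leaves pain unexamined.

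**Separately, in either case.** Reconcile the hospitalization sentence in Section 4.4.2 with the inpatient requirement in Sections 5.2 and 6.

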4.3.2 Secondary Outcome Variable

Health-related quality of life, assessed via the PedsQL total score and its domain-specific subscales (physical, emotional, social, school), as well as physical health summary score and psychosocial health summary score will examine the broader impact of sleep disturbances. This will help determine, for example, whether poor sleep in children with cancer correlates with reduced emotional or physical functioning compared to other groups.

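### Section 7 relates PSQI to PedsQL by correlation only; a regression on PSQI, group, age, gender and parental education, all already collected, would serve this secondary aim better at little cost

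*Protocol*

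**What the plan says.** Section 7 plans three things that bear on this point.

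- A one-way ANOVA compares the level of each scale across the three groups.
- In a secondary analysis, "multiple linear regression will examine the relationships between sleep quality (PSQI score) and potential predictors (e.g., type of cancer treatment, pain levels", and this is done "while adjusting for confounding factors such as age, gender, and socioeconomic status (SES". PSQI is the outcome there, and PedsQL is not named.
- For the link between the scales, "Pearson or Spearman correlations will be utilized to assess the relationships between PSQI and PedsQL scores", with the purpose of "helping to evaluate the impact of sleep disturbances on health-related quality of life". No covariates, grouping or comparison between groups are stated.

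Section 4.2.2 describes PedsQL as "enabling exploration of how sleep disturbances correlate with broader well-being in children with cancer, other chronic illnesses, and healthy controls", and says that it "will serve as a secondary measure to explore how sleep disturbances correlate with broader quality-of-life outcomes". Section 4.3.2 gives as an example "whether poor sleep in children with cancer correlates with reduced emotional or physical functioning compared to other groups".

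Section 4.3.3 lists the variables collected to control confounding: "age (in years), gender, socioeconomic status (SES), disease type, disease status, and use of hypnotics (yes/no". SES is parental education in four categories. That section says that these factors may influence sleep, and calls for adjustment so that the effect of chronic illness on sleep can be isolated.

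**The concern.** A bivariate correlation adjusts for nothing. The children are 6 to 18 years old, and Section 4.3.3 itself expects age and parental education to affect sleep. Under Sections 4.2.1 and 4.2.2 the respondent also changes from parent to child with age, on both scales. Age is therefore a plausible shared source of variation in PSQI and PedsQL, and the plan's correlation would count that variation as association.

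If the correlation is pooled, group is a second shared source. Section 4.4 expects children with cancer to sleep worst and healthy children best. If quality of life follows the same order, group differences alone produce a negative correlation.

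What is at stake is how the secondary sleep-quality-of-life result is read, especially as Section 7 describes it as bearing on impact. A one-time survey can show association only, whatever the model.

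**Working it through.** The protocol gives no expected correlation, SD or group difference, so it has no figure of its own to reproduce. From the documents: 50 children per group, 150 in all, and alpha 0.05 (two-sided assumed). All correlations and gaps below are assumptions.

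**1. Pooled correlation.** Let the cancer and healthy groups differ by gx SD on PSQI and by gy SD in the opposite direction on PedsQL, with the chronic-illness group midway. Three equal groups at -g/2, 0 and +g/2 have between-group variance (g²/4 + 0 + g²/4)/3 = g²/6. With within-group correlation rw,

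r(pooled) = (rw - gx·gy/6) / sqrt[(1 + gx²/6)(1 + gy²/6)].

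| gx, gy | rw | pooled r | p<0.05 (20,000 simulated studies) |
|---|---|---|---|
| 0.5, 0.5 | 0 | -0.0417/1.0417 = -0.04 | 7.9% |
| 1.0, 1.0 | 0 | -0.1667/1.1667 = -0.14 | 41.6% |
| 1.0, 0.5 | 0 | -0.0833/sqrt(1.1667 × 1.0417) = -0.08 | 15.1% |
| 1.0, 0 | 0 | 0 | 5.0% |
| 1.0, 1.0 | -0.3 | -0.4667/1.1667 = -0.40 | – |

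In the rows with rw = 0, a model with group as a factor rejects in 4.9% to 5.1%. The excess counts as error only if the within-group association is the target.

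**2. Age confounding within a group.** If age correlates +a with PSQI and -a with PedsQL and nothing else links them, the induced correlation is -a². At n=50:

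| a | induced r | p<0.05 |
|---|---|---|
| 0.2 | -0.04 | 5.8% |
| 0.3 | -0.09 | 9.5% |
| 0.4 | -0.16 | 19.8% |

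By-group reporting therefore removes the problem in step 1 but not this one.

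**3. Precision.** Fisher z intervals at r = -0.3, with atanh(0.3) = 0.3095. The adjusted model uses 7 covariate df (group 2, age 1, gender 1, education 3), so its effective n is 150 - 7 - 3 = 140.

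| Estimate | half-width on z | 95% CI | width |
|---|---|---|---|
| One group, n=50 | 1.96/sqrt(47) = 0.286 | -0.534 to -0.024 | 0.510 |
| Pooled, unadjusted, n=150 | 1.96/sqrt(147) = 0.162 | -0.439 to -0.147 | 0.292 |
| Common, adjusted, n=150 | 1.96/sqrt(140) = 0.166 | -0.442 to -0.143 | 0.299 |

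The adjusted interval is 0.299/0.510 = 59% as wide as a single group's. That comes entirely from using 150 children under a common slope; against the plain pooled correlation, adjustment gains nothing in width.

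**4. PSQI × group term.** In the full covariate model (20,000 runs), the 2-df test has power 17% for within-group correlations of -0.3, -0.3, -0.5 and 36% for -0.3, -0.3, -0.6. With a wider spread (-0.6, -0.3, -0.1; 4,000 runs with SES as a single continuous covariate) it is about 65%. Equal correlations also need not mean equal slopes: with r = -0.3 in every group but PedsQL SDs in the ratio 1.5/1.25/1 or 2/1.5/1, the test rejects in 8% and 13% of 4,000 runs.

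**The case against.** The strongest reply is that this rests on silence. Section 7 does not say that the correlation is pooled, and grouping and covariates for an exploratory correlation are often left to an analysis plan. Sections 4.2.2 and 4.3.2 speak of how the scales correlate, and a correlation answers that. This holds in part. It cannot be said that the plan will pool; Section 4.2.2, which names all three groups, leans towards by-group correlations. But the protocol does choose the method, and it states adjustment for the neighbouring regression and not for this analysis. The lack of age, gender and SES adjustment applies whether or not the groups are pooled.

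Some stronger readings are tempting and should be resisted.

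- A reader might infer that the plan cannot answer its own question in Section 4.3.2. That example may ask whether the association differs in cancer, or only whether functioning is lower in cancer, which the ANOVA covers. The text does not settle it.
- A reader might infer that regression buys precision. Step 3 shows that adjustment does not.
- A reader might expect three by-group p-values to be set against each other as if they compared the groups. The protocol does not say that it will do this.

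The reply also rightly asks more of the remedy. A model of PedsQL total alone would leave unadjusted the emotional and physical scores that Section 4.3.2 names. Because healthy controls may be siblings of enrolled patients (Sections 5 and 5.3), one model may contain related children. Both are dealt with in the change proposed below.

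**Conclusion.** The point holds as a cheap improvement to a secondary, exploratory analysis. The only stated link between PSQI and PedsQL is an unadjusted correlation, although group, age, gender and parental education will all be available.

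The size depends on assumptions that the protocol neither supports nor excludes. Confounding by age alone is slight at a = 0.2 to 0.3 (6% to 10% against a nominal 5%) and material at 0.4 (20%). Pooling is nearly harmless at gaps of 0.5 SD on both scales (8%), serious at 1 SD (42%), and harmless if PedsQL does not differ between groups.

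No contradiction in the protocol is shown, and the primary PSQI comparison is unaffected. The case for a formal comparison of slopes between groups is weaker: the protocol may not ask for it, and 50 per group gives it low power unless the groups differ widely.

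**What to change.** In Section 7, replace the correlation sentence with text to this effect:

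*The association between PSQI global score and PedsQL total score will be estimated by linear regression of PedsQL total on PSQI, group, age, gender and parental education, with robust standard errors, clustered by family where a healthy control is a sibling of an enrolled patient. The same model will be fitted to the physical and emotional scores as exploratory outcomes. Pearson or Spearman correlations will be shown by group with 95% CIs as description. A PSQI × group term may be added to give exploratory group-specific slopes with 95% CIs; no conclusion will rest on its p-value.*

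Replace the word impact with association.

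Cost: a wording change, one main model and its two exploratory repeats. No new questionnaire items are needed, though siblings must be linkable by a family code. The model spends about 7 covariate df, leaving 150 - 1 - 1 - 7 = 141 residual df (139 with the interaction) against 148 for a pooled correlation. The main estimate loses the rank-based option, so residuals should be inspected; the by-group Spearman coefficients remain as a descriptive check.
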